
4.2 RATIONALE

4.2.1 Study design

DRI11772 study will consist of the evaluation of the efficacy and safety of 2 dose levels/regimens of SAR156597 administered subcutaneously over a 52-week treatment period and, the determination of the optimal dose level/regimen for the treatment of patients with IPF.

It will be a multinational, randomized, double-blind, placebo-controlled, 3-parallel group study conducted in out-patients suffering from IPF according to the American Thoracic Society/ European Respiratory Society/ Japanese Respiratory Society/ Latin American Thoracic Association (ATS/ERS/JRS/ALAT) guideline criteria and confirmed by a multidisciplinary panel of experts in IPF.

Patients who discontinue treatment during the study will be followed for the full planned 52 week duration of the study in order to ensure the collection of efficacy outcomes on all randomized patients and minimize the potential for bias in analyses due to missing data.

4.2.2 Design rationale

The 52-week treatment duration is based on published data from clinical trials in IPF and also from IPF natural history data that respectively showed evidence for treatment-induced changes on surrogate endpoints and significant decline in respiratory function characteristic of disease progression over a 12-month period.

The follow-up period of 12 weeks after dosing for adverse events (AEs) and pharmacokinetic (PK) analysis is appropriate taking into account the estimated half-life of about 11 to 15 days for SAR156597 from the TDU11325 and TDR11326 studies.

Dose selection

SAR156597 was safe and well tolerated at single SC doses up to 300 mg in healthy subjects as well as at repeated SC doses up to 200 mg during 6 weeks in patients with IPF, including at the injection site level.

No *in vivo* data from an appropriate animal model of IPF is available to guide the desired pharmacologically active exposure of SAR156597. However, modelling and simulation of the inhibition of Stat6 phosphorylation in monkey suggest that its inhibition will be fully achieved. Additionally, SAR156597 has been shown to reduce in a dose dependent manner (up to 200 mg once a week) the plasma level of TARC, a protein biomarker involved in the IL-4/IL-13 pathway, after 6 weeks of treatment in patients with IPF.

As the desired dose frequency for patient convenience is once every 2 weeks, the weekly dose regimen for the 200 mg dose level will be compared to the every 2 weeks dose regimen for 200 mg.

Finally, modelling and simulations based on the PK data from the multiple dose clinical study (TDR11326) have confirmed that a 200 mg dose administered once every 2 weeks and once a week give an acceptable safety margin in terms of exposure ratio (monkey AUC at NOAEL/human AUC) of ~6 and ~3 respectively.

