5 STUDY OBJECTIVES

5.1 PRIMARY

To evaluate, in comparison with placebo, the efficacy of 2 dose levels/regimens of SAR156597 administered subcutaneously during 52 weeks on lung function of patients with IPF.

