11 STATISTICAL CONSIDERATIONS

11.1 DETERMINATION OF SAMPLE SIZE

Approximately 300 patients will be randomized in this study, 100 per treatment group. Based on the enrollment in prior studies of this population approximately half of the patients are expected to be older than 65.

The sample size calculations are based on the primary efficacy variable of % predicted FVC change from baseline to week 52, with the following assumptions:

- A common standard deviation of 12% is assumed based on the data from previous trials (26)
- A 5 % mean difference between each dose and placebo in change from baseline in % predicted FVC
- A 2-sided 5% significance level with 80% power

Ninety two (92) patients per treatment group will yield 80% power to detect a 5 percentage point difference between the treatment groups and placebo. Additional patients will be randomized in each regimen to allow for dropouts; therefore, approximately 100 patients will be randomized into each treatment group, for a total sample size of approximately 300 patients for the study.

As a rank-based method will be used for analysis the actual power may differ from these calculations, however, calculations based on the ASCEND study (28), which used the same analysis method and endpoint confirm that the planned analysis should have at least 80% power. No adjustment is made for multiplicity since a hierarchical testing procedure is proposed.

Calculations were made using nQuery Advisor 7.0

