### 2.4.4.1 Analysis of primary efficacy endpoint(s)

The primary efficacy endpoint will be analyzed on the mITT population. In the primary analysis, assessments at week 52 will be used regardless of whether the patient has previously discontinued treatment.

Due to the non-normality of the endpoint distribution, the absolute change from baseline in % predicted FVC at week 52 as defined in [Section 2.1.3.1](#) will be analyzed in the mITT population using a rank ANCOVA model adjusted on the stratification factor (with/without background therapy). This model will use the ranks of absolute change from baseline to week 52 in % predicted FVC as the outcome and the ranks of baseline % predicted FVC as a covariate. In case of ties, the mean of the corresponding ranks will be assigned.

To summarize, the following steps will be performed:

A) On the pool of arms SAR156597 200mg qw and placebo:

1. Imputation of missing data at 52 weeks

a) Week 52 missing values due to reasons other than death or lung transplant

- i. Patients in active arm and taking treatment at 52 weeks: Missing values at 52 weeks will be imputed using a model estimated from the subset of patients in the active arm who completed the 52-week treatment period and with a week 52 value. The imputation model will be based on a Mixed Model with Repeated Measures (MMRM) with fixed categorical effect of stratification factor (with/without Background Therapy) and repeated categorical effect for time point (baseline, week 12, week 24, week 36, week 52). Parameters will be estimated with the Newton-Raphson algorithm, an unstructured covariance matrix will model the within-patient errors, and the denominator degrees of freedom will be estimated using Satterthwaite's approximation. Missing values at 52 weeks will be imputed using the empirical best linear unbiased prediction (EBLUP).

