- Finally, all the results will be combined thanks to Rubin's rule.
- The particularity of this approach is that it will takes into account the disease progression:
  - Before withdrawal, all patterns have the same profile. A patient will be assumed to have the same mean response as his/her treatment arm.
  - After withdrawal (which results in missing values for all subsequent visits):
    - a patient in placebo arm will be imputed as in MAR framework.
    - a patient in active arm will be imputed assuming that the advantage due to past treatment is incremented with placebo slope assessed from withdrawal visit to imputed visit.

- In practice:
  - When running the imputation model, if the absolute change from baseline calculated from the predicted week 52 value is greater than zero (increases above baseline), it will be set to zero.
  - The MMRM will be performed on each imputed dataset.
  - The Rubin's rule will be performed using Roger's macro or MIANALYZE SAS procedure as appropriate
    - The number of datasets (1000 if appropriate) will be chosen to achieve p-value stability.

Week 52 missing data due to death or lung transplant will be imputed using the distribution of their last available % Predicted FVC assessment. The mean (SD) will be calculated and then, for each dead or lung transplanted patient, a value will be drawn several times (same number as for CIR methodology) between this mean and 0 (translation of this distribution with mean as maximal value achievable and right truncated at 0 if required). If the value drawn is higher than the last available patient's value, the imputed week 52 value will be set to the last available patient's value.

The SAR156597 qw arm will be tested versus Placebo at a type I error level of 5% first and if significant, will the SAR156597 q2w arm be tested versus Placebo at a two-sided type I error level of 5% using the appropriate contrast. The adjusted Least Square Means (LSMeans) estimates and standard errors (SE) will be provided for each of the 3 arms, adjusted differences of means (LSMEAN differences), corresponding standard errors (SE), 90% and 95% CIs will be assessed for each active arm versus placebo.

A specific table will describe the following items by treatment arm:

- The number (%) of patients with an observed week 52 value for % predicted FVC
  - The mean (SD) and median (Q1:Q3) of baseline and week 52 values of % predicted FVC for those patients

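### The protocol announces a comparison of 200 mg weekly with 200 mg every two weeks, but no efficacy analysis estimates that difference

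*Protocol*

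**What the plan says.** The protocol title calls the study dose-ranging. Section 4.2.1 lists among its purposes "the determination of the optimal dose level/regimen for the treatment of patients with IPF". The dose-selection paragraph of 4.2.2 notes that dosing every two weeks is the more convenient schedule for patients, and so "the weekly dose regimen for the 200 mg dose level will be compared to the every 2 weeks dose regimen for 200 mg".

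The objectives and analyses are framed differently:

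- **Primary objective (Protocol 5.1):** "To evaluate, in comparison with placebo, the efficacy of 2 dose levels/regimens of SAR156597". The secondary efficacy objective on disease progression is also against placebo.
- **Sample size (Protocol 11.1):** the design effect is "A 5 % mean difference between each dose and placebo in change from baseline in % predicted FVC". No difference between regimens is assumed.
- **Primary analysis (SAP 2.4.4.1):** run twice, first "On the pool of arms SAR156597 200mg qw and placebo", then on the two-weekly arm and placebo.
- **Sensitivity models (SAP 2.4.4.1.1):** least-squares means for each of the three arms, but for differences, "90% and 95% CIs will be assessed for each active arm versus placebo".
- **Disease progression and mortality (SAP 2.4.4.2.1, 2.4.4.2.2):** hazard ratios for each active arm against placebo.
- **Multiplicity (Protocol 11.4.2.3, SAP 2.4.4.3):** weekly against placebo first; two-weekly against placebo only if the first is significant.

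**The concern.** The protocol states a between-regimen question, and the trial will hold the randomized data to estimate the answer, but no efficacy output is specified that does so. Table 1 of the SAP says the Week 52 analysis will inform a benefit/risk evaluation and the decision to move to Phase 3. At that point the formal efficacy evidence on regimen would be two separate results against placebo. One result being significant and the other not says little about whether the regimens differ. If both are significant, the two tests do not show whether the more convenient schedule gives up efficacy. The primary ranks cannot be compared across regimens either, because they are formed in two separate pools.

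**Working it through.** **Inputs (Protocol 11.1, repeated in SAP 1.3).** "A common standard deviation of 12% is assumed based on the data from previous trials"; "A 2-sided 5% significance level with 80% power"; a 5-point effect of each dose against placebo; 92 patients per arm for 80% power; about 100 per arm randomized. The true effects assumed for the two regimens below are mine: 5 points is the design value and 4 points shows the range.

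**1. Reproduce the plan's figure.**
n per arm = 2 × 12² × (1.960 + 0.842)² / 5² = 90.4, rounded up to 91 by the normal approximation. A noncentral t calculation gives 79.8% power at 91 and 80.3% at 92. The stated 92 is reproduced, for a comparison with placebo.

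**2. Precision of a direct weekly minus two-weekly contrast.**
SE = 12 × √(2/n); 95% half-width = 1.96 × SE.

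| n per arm | SE | 95% half-width | Power, true difference 2 | Power, true difference 3 | Power, true difference 5 |
|---|---|---|---|---|---|
| 92 | 1.77 | 3.47 | 20% | 40% | 81% |
| 100 | 1.70 | 3.33 | 22% | 42% | 84% |

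Eighty per cent power for a 3-point difference between regimens would need 252 per arm. The contrast can be estimated here, but a moderate difference cannot be tested with adequate power.

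**3. What the results against placebo say when the regimens are equally effective.** I simulated three normal arm means with a shared placebo arm, giving both regimens the same true effect, and tested each against placebo at two-sided 5%.

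| True effect in both | n per arm | Weekly significant, two-weekly not | As a share of trials where weekly is significant | Direct contrast significant within the weekly-only trials |
|---|---|---|---|---|
| 5 | 92 | 11.0% | 14% | 14% |
| 5 | 100 | 9.8% | 12% | 15% |
| 4 | 92 | 15.9% | 26% | 12% |
| 4 | 100 | 15.3% | 23% | 13% |

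At 5 points and 92 per arm, both regimens are significant in 69.7% of trials. In a further 11.0% the two-weekly arm is nominally significant but cannot be claimed, because the weekly arm failed first.

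**4. Search for the comparison elsewhere.** The sample size, primary analysis, sensitivity analyses, subgroup analyses and forest plots, disease progression, mortality and exploratory endpoints (including the added DLCO analysis) contain no test, difference, ratio or interval for weekly against two-weekly.

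**The case against.** The strongest reply is that 4.2.2 is a design rationale. It can be read as explaining why two frequencies were included rather than as promising a contrast, and the formal efficacy objectives are against placebo, which the analyses match. This is a fair reading, and it is why rewording is an acceptable remedy. It does not remove the mismatch, since 4.2.1 separately names finding the optimal regimen as part of the study.

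A reader might infer that every planned analysis is against placebo. That is not so. The SAP plans least-squares means for each arm, Kaplan-Meier curves by arm, and PK, anti-drug antibody and biomarker summaries by arm. The protocol synopsis has safety compared qualitatively between groups, and population PK is reported separately. From the per-arm means and standard errors a reader could subtract and approximate an interval. None of this is a specified regimen contrast with its own confidence interval, and the hazard ratios are against placebo only.

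The other fair point is that the interval is wide. With an observed difference of zero, differences above 2 points in either direction would remain open, and Protocol 9.5 treats a 2-6% decline as clinically important. That limits the contrast to estimation, but it is no reason to leave it unspecified.

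**Conclusion.** The point holds as a gap between stated purpose and planned efficacy analysis. It does not affect the validity of the primary test or the type I error control, so the change is a low-cost improvement.

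Its size: with equal true effects of 5 points, the weekly-only pattern arises in about 10-11% of trials (about 15-16% at 4 points), and a direct contrast would be significant in only about 14% of those (about 12% at 4 points). These figures assume normal outcomes, SD 12 in every arm, 92 to 100 evaluable patients per arm and no covariate adjustment. The rank-based primary analysis will differ somewhat.

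A reader might go further and infer that the regimen will be chosen by which one reaches p<0.05. The documents do not say so. They give no selection rule, and the SAP refers to a benefit/risk evaluation. Nor could the two-weekly regimen be the only one declared significant: under the hierarchy the possible formal results are neither, weekly only, or both.

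**What to change.** - **SAP 2.4.4.1.1:** in the three-arm repeated-measures models of Sensitivity analyses 1 and 2, add the weekly minus two-weekly least-squares mean difference at Week 52 with its 95% CI.
- **SAP 2.4.4.2.1:** add the weekly versus two-weekly hazard ratio for disease progression with its 95% CI, from a Cox model that includes all three arms.
- Label both as estimation only, outside the alpha hierarchy.

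The cost is a few lines of SAP text and one contrast per model. It needs no alpha, patients or visits. The downside is that a half-width of about 3.3-3.5 points may not separate the regimens, and the report must state this so that a wide interval is not read as equivalence.

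If the sponsor does not intend a between-regimen comparison, the alternative is to reconcile Protocol 4.2.1 and 4.2.2 with the placebo-only objectives and analyses.

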4.2.3 Rationale for the use of outcome measures

4.2.3.1 Pulmonary Function Tests (PFTs)

Pulmonary function tests (PFTs) will be assessed during the study. Pulmonary function tests, such as spirometry and carbon monoxide diffusing lung capacity (DLCO), are standard evaluations for patients with IPF. Changes in forced vital capacity (FVC) and DLCO have been shown to be correlated with survival (17).

4.2.3.2 Six-Minute Walk Test (6MWT) and Pulse Oximetry

The 6-MWT with oximetry will be used in this study. It is a safe and reproducible procedure for patients with IPF. Baseline desaturation during a 6MWT is a powerful predictor of subsequent mortality (18)

4.2.3.3 Lung High Resolution Computed Tomography (HRCT)

A significant correlation between high-resolution computed tomography (HRCT) visual score and lung function tests both at diagnosis and at follow-up has been shown and reported in the literature. The HRCT study is able to identify and quantify anatomic IPF and also to evaluate the progression of the disease. In clinical practice, the HRCT visual score of disease extent can be used in association with function tests to monitor IPF evolution, and to evaluate prognosis and therapy (19).

4.2.3.4 St George Respiratory Questionnaire (SGRQ)

Impact of IPF on quality of life will be assessed using the SGRQ (20). This questionnaire covers the measurement of symptoms, activity, and impacts. It has good discriminative and evaluative properties and is responsive to therapeutic trials. It takes 8 to 15 minutes to complete.

4.2.3.5 EuroQol Questionnaire, 5 level system (EQ-5D-5L)

The EQ-5D is a standardized instrument for use as a measure of health outcome.

EQ-5D-5L is the 5-level system for the 5-dimensional format of the EQ-5D and covers the measurement of mobility, self-care, usual activities, pain/discomfort and anxiety/depression.

EQ-5D-5L is designed for self-completion by subjects, taking less than 5 minutes to complete.

Instructions to respondents are included in the questionnaire.

4.2.3.6 Biomarkers

Peripheral blood will be collected for measurement of protein biomarkers in serum or plasma. The protein biomarkers have been selected either based on their potential link with SAR156597 mechanism of action, based on reported association with survival in or pathogenesis of IPF or lung fibrosis. These include, but are not limited to, inter-cellular adhesion molecule 1 (ICAM1), TARC, periostin and Human Epididymis protein 4 (HE4). In a previous observational longitudinal study (ASY12295), some of these biomarkers showed a higher circulating concentration at baseline in IPF patients compared to healthy controls, with estimated AUROC above or close to 0.8. On exploratory basis, the correlation between IPF disease biomarkers and lung function progression will be assessed at Week 24 and Week 52. Moreover, in another previous clinical study with increasing doses of SAR156597 (TDR11326) promising results were observed for some of these markers, e.g. a trend in reduced blood concentration of TARC with increasing doses of SAR156597. Drug-related protein biomarkers will be assessed at baseline, Week 24 and Week 52 to look for an effect on these proteins after 6 months and 12 months of SAR156597 treatment.

Additional blood samples will be archived for potential future assay of protein and mRNA biomarkers related to the diagnosis, progression, or therapeutic responsiveness of IPF

4.2.3.7 Genetic testing

The genetic basis of IPF is not well understood. Polymorphisms of various genes encoding for cytokines and mucins have been reported to be increased in sporadic IPF. To obtain a better understanding of IPF pathogenesis and disease course in relation to the genomic profile, blood samples will be collected to further characterize the genotype of IPF subjects by analysis of a subset of selected genes already associated to IPF including but not limited to IL4 (21), IL4R (22), STAT6 (23) and MUC5B (24).

5 STUDY OBJECTIVES

5.1 PRIMARY

To evaluate, in comparison with placebo, the efficacy of 2 dose levels/regimens of SAR156597 administered subcutaneously during 52 weeks on lung function of patients with IPF.

5.2 SECONDARY

- To evaluate the efficacy of 2 dose levels/regimens of SAR156597 compared to placebo on IPF disease progression
- To evaluate the safety of 2 dose levels/regimens of SAR156597 compared to placebo in patients with IPF
- To evaluate the pharmacokinetic profile of SAR156597 200 mg administered subcutaneously every week and every two weeks during 52 weeks
- To assess the potential immunogenicity of SAR156597
- To evaluate the effect of SAR156597 on circulating biomarkers
- To explore the effect of SAR156597 on quality of life

6 STUDY DESIGN

6.1 DESCRIPTION OF THE PROTOCOL

This study will be a multinational, randomized, double-blind, placebo-controlled, 3 parallel groups study to assess the efficacy and safety of SAR156597 200 mg once a week and 200 mg once every two weeks administered subcutaneously over a 52 week period to patients with IPF.

Approximately 300 patients will be randomized in a ratio 1:1:1 to the following three treatment arms:

- SAR156597 (qw) arm (n=100):

Patients will receive SAR156597 administered subcutaneously in 200 mg doses once every week (qw)

- SAR156597(q2w) arm (n=100):

Patients will receive SAR156597 administered subcutaneously in 200 mg doses once every 2 weeks (q2w) alternating with placebo subcutaneously once every 2 weeks

- Placebo (qw) arm (n=100):

Patients will receive placebo subcutaneously once every week.

The study population will be stratified at baseline according to a background therapy with pirfenidone or nintedanib (standard of care for IPF in authorized countries).

For a schematic presentation and a detailed flow chart, please refer to [Section 1.2](#).

6.2 DURATION OF STUDY PARTICIPATION

6.2.1 Duration of study participation for each patient

The study will last up to 68 weeks as follows:

- Up to 4 weeks of screening
- 52 weeks of study treatment
- 12 weeks of follow-up

6.2.2 Determination of end of clinical trial (all patients)

The end of the clinical trial is defined as the day the last patient completes his/her last visit planned in the protocol.

6.3 STUDY COMMITTEES

Central review of clinical documentation

Clinical documentation such as patient history, HRCTs, and histology will be centrally reviewed by a radiologist and a pathologist specialized in interstitial lung diseases in order to confirm the diagnosis of IPF. HRCTs performed during the course of the study will also be reviewed and scored on a blinded basis to appropriately assess the changes over time.

Data Monitoring Committee

A Data Monitoring Committee (DMC) will be charged with monitoring the safety of the patients participating in this clinical trial. This committee is comprised of externally-based individuals with expertise in the diseases under study, biostatistics, or clinical research. The DMC will, in due time, give appropriate recommendations to the Sponsor on safety aspects during the conduct of the study, if needed. The DMC is justified by the early stage of development of SAR156597 that has gathered sparse safety information in patients with IPF so far [REDACTED]. The DMC responsibilities and the data review processes are fully described in the DMC charter. In the above capacities, the DMC is advisory to the Sponsor. The Sponsor is responsible for promptly reviewing and for taking into account in a timely manner the recommendations of the DMC in terms of trial continuation with or without alterations or of potential trial termination

Operational Committee

An Operational Committee will be put in place for potential consultation on unexpected ethical, methodological, or technical questions that may arise during the course of the study.

